Secondary Aim: Define the effects of NMES on self-reported physical function and quality of life at 4 weeks from baseline. We hypothesize that NMES will improve quality of life and self-reported physical function compared to the control.

METHODS AND PROCEDURES

Study Design: Describe the research design, including a description of any new methodology and its advantage over existing methodologies.

Study design: We will use a randomized-controlled trial design. Patients admitted for heart failure will be recruited and randomized to NMES or control for 4 weeks following hospital discharge. Patients will be stratified by sex and age. Baseline testing will occur prior to discharge and consist of functional assessment by 6MW and SPPB and completion of 2 questionnaires regarding quality of life and physical function (Kansas City Cardiomyopathy questionnaire {KCCQ} and (Medical Outcomes Study Short Form-36 {MOS SF-36}). After completion of the 4 week intervention period, patients will undergo Post-Testing which will be identical to Baseline testing.

Inclusion/Exclusion Criteria: Patients will be recruited if they: 1) have clinical diagnosis of heart failure being actively managed during hospitalization, 2) live within 30 miles of UVMMC and are between 50-90 years of age. Patients will be excluded if they have: 1) severe dementia/alzheimer's disease 2) an active malignancy, excluding non-melanoma skin cancer or low-grade prostate cancer under active surveillance; 3) exercise-limiting vascular or neuromuscular disease; 4) body mass index $\geq 40 \text{ kg/m}^2$ or 5*) an existing lower extremity blood clot or implantable cardioverter-defibrillator (ICD) or pacemaker (PPM).¹⁴ *The last criteria is a contraindication for NMES and we will withdraw patients if they develop a blood clot or receive an ICD or PPM.

Randomization and blinding: Patients will be randomized prior to hospital discharge to NMES or control using Pocock and Simon's covariate-adaptive randomization for which sex and age will be stratified. The unblinded project manager will train patients to use NMES device and oversee them during the intervention. The PI and co-I will be blinded to treatment assignment.

Interventions:

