Usual care: Patients will not receive an NMES device. We opted not to use "sham" stimulation (eg, low-intensity stimulation below the threshold to initiate contraction) lessen the chance that patients may increase stimulation to produce contractions if there is perceived benefit. Patients will be contacted weekly to assess overall recovery. As there is currently no standard of care rehabilitation for these patients following discharge and NMES does not have demonstrated benefits, our study meets the requirements for clinical equipoise.

NMES: NMES will be carried out bilaterally on the quadriceps using a portable stimulator. Two adhesive electrodes will be placed to the anterior surface of each thigh. Symmetrical, biphasic pulses (400 μ s duration at 25 Hz) will be used, with a duty cycle of 25% (10 s on, 30 s off). Patients will be trained to conduct NMES sessions and will select stimulation intensities sufficient to cause visible muscle contractions below their pain threshold. Training in the use of the NMES device will begin prior to hospital discharge. After discharge, NMES sessions will occur 5 d/wk once per day for 45 min per occasion (5 min low-intensity warm-up, 40 min higher-intensity stimulation) for 4 wks. This program is meant to mimic an aerobic-type exercise stimulus and similar to prior protocols. Daily logs and weekly phone calls will be used to monitor compliance to maximize intervention fidelity with overall compliance measured using the device software.

Outcomes: The primary outcome is 6MW. Functional capacity measures and quality of life measures will be obtained at baseline (prior to hospital discharge) and at 4 weeks.

1. Baseline characteristics including age, body mass index, length of hospital stay, medications, and smoking status
2. Functional Capacity measures:
 - a. 6-MW test is a well-validated method to assess functional capacity in patients with cardiac disease and shows convergent validity with other indices of physical function. The test will be conducted under standardized conditions, as described by us.^{11,15} Distance walked (m) will be the primary outcome.
 - b. SPPB will be measured, as it is a widely used, easy to measure index of physical function in older adults. Thus, it provides context for the severity of disability in our population and the modifying effects of NMES for comparison to other studies.¹¹
3. Quality of Life measures:

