The proposed sample of 60 participants is based on having sufficient power to calculate differences in our primary outcome (6MW) between the control condition and the intervention and accommodating for potential drop outs (20%) from the study.¹¹ Power is estimated to be 80% to detect a difference in the change in 6MW between the 2 groups at the $p<0.05$ level. These estimates are based on data from a meta-analysis of RCTs of NMES in *stable* patients with chronic heart failure which detected a difference of 47 m between NMES group vs placebo as well as our pilot data of CABG patients, where patients randomized to NMES increased 6-MW distance 73 m further than controls.¹¹ We assume a 6-MW distance of 250 ± 60 m (mean \pm SD) at hospital discharge in both groups. Additionally, we have reduced the improvement in 6-MW distance in the NMES group by ~30% to 50 m (6-week post-discharge NMES: 250 ± 60 m vs. Control: 300 ± 60 m) to be conservative. This magnitude improvement in 6-MW is similar to meaningful changes found in 6-MW performance in older adults with mild- to moderate mobility disability undergoing home-based strength training (47 m) and is twice the minimal clinically significant difference in patients with cardiac disease following CR (25 m).¹⁸ Therefore, we will need to recruit 60 patients with our target of 48 patients to complete the study (n=24/group), assuming a drop out of 20%. We have not performed sample size estimates for SPPB or secondary outcomes, as extrapolating the ability of NMES to affect other variables is challenging barring relevant preliminary data, particularly in *recently hospitalized* heart failure patients.

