Data Safety and Monitoring: The specific design of a Data and Safety Monitoring Plan (DSMP) for a protocol may vary extensively depending on the potential risks, size, and complexity of the research study. For a minimal risk study, a DSMP could be as simple as a description of the Principal Investigator's plan for monitoring the data and performance of safety reviews or it could be as complex as the initiation of an external, independent Data Safety and Monitoring Board (DSMB). The UVM/UVM Medical Center process for review of adverse events should be included in the DSMP.

Drs. [name] and [name] will monitor the safety of the research procedures for this study. We have not set up a formal safety committee for several reasons. First, the PIs and the investigative team have a long history of performing the measurements proposed in this proposal. The procedures carry relatively low risk to the volunteers. Second, because of the small number of patients and track record of performing these procedures, it is highly unlikely that we will need to "stop" the study or significantly

alter the procedures. If any problems/unanticipated events arise related to the NMES intervention, [name] will determine the nature of the problem and its relatedness to the NMES intervention and decide whether continued participation in the study is in the best interest of the patient. As detailed above, however, NMES is FDA-approved for this indication and we have taken precautions to minimize the potential for adverse effects.

Adverse Event and Unanticipated Problem (UAP) Reporting: *Describe how events and UAPs will be evaluated and reported to the IRB. All protocols should specify that, in the absence of more stringent reporting requirements, the guidelines established in the Committees on Human Research "Adverse Event and Unanticipated Problems Reporting Policy" will be followed. The UVM/UVM Medical Center process for review of adverse events and UAPs to subjects or others should be included in the DSMP.*

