Adverse events will be reported by one of 3 mechanisms. First, the joint University of Vermont/University of Vermont Medical Center (UVMMC) Committee for Human Subject Research Adverse Event Reporting Document. These reports will be sent to the office of the Committee for Human Research in the Medical Science (CHRMS) within 2 days of the event. Reporting any adverse events will be the responsibility of the PIs. The CHRMS will make a determination as to whether additional reporting requirements are indicated. Additionally, the UVMMC Patient Safety Reporting system (SAFE), which may be initiated by health care center staff or study personnel. These forms will be forwarded within 3 days to the PI, UVMMC Risk Management Office, CHRMS and other appropriate agencies, as indicated by the nature of the report. Reviews of protocol specific adverse events will be performed no less than annually. Additionally, any adverse event that occurs will be forwarded to the PIs for reporting to the Human Subject Research Protection Office within 1 week of occurrence. Of note, these protections against risk include both physical risks to the volunteers, as well as risks associated with any breach in confidentiality.

On an annual basis, Drs. [name] and [name] will assess data being gathered and safety of volunteers to assess the pattern or frequency of events to identify occurrence of any event or problem that alters the safety profile of the procedures being performed. The exception would be occurrence of a serious adverse event or unanticipated problem that necessitates re-evaluation of the expected risk of the study procedures at an earlier time point. Additionally, they will evaluate data collection and storage to ensure the confidentiality of data and quality. Each of these evaluations will be followed by reports of study progress and patient safety to the University of Vermont CHRMS via yearly progress reports.

Withdrawal Procedures: *Define the precise criteria for withdrawing subjects from the study. Include a description of study requirements for when a subject withdraws him or herself from the study (if applicable).*

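### The only scheduled look at adverse events across patients is annual, although each patient is treated for 4 weeks; a cheap patient-count trigger would make its timing independent of the unstated accrual rate

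*Combined protocol and SAP*

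**What the plan says.** The Adverse Event and Unanticipated Problem (UAP) Reporting section of the combined protocol and SAP sets a minimum frequency: "Reviews of protocol specific adverse events will be performed no less than annually". It then says that two investigators, once a year, "will assess data being gathered and safety of volunteers to assess the pattern or frequency of events". One route to an earlier look is given: "The exception would be occurrence of a serious adverse event or unanticipated problem that necessitates re-evaluation" of the expected risk. No review is tied to the number of patients enrolled or treated.

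Under Data Safety and Monitoring the plan states "We have not set up a formal safety committee for several reasons", citing low risk, small numbers and experience with the procedures. The reporting section adds that the study as a whole has no stoppage criteria.

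On exposure, the Study Design section has patients "randomized to NMES or control for 4 weeks following hospital discharge", and the Interventions section says "NMES sessions will occur 5 d/wk once per day for 45 min per occasion". The Sample Size Calculation section plans 60 recruited patients, 48 completers and 24 completers per group. No recruitment period or accrual rate is given.

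**The concern.** The yearly review has a stated purpose: "to assess the pattern or frequency of events to identify occurrence of any event or problem that alters the safety profile" of the procedures. To serve patients in this trial, it has to come while some of them are still to be treated. A 12-month interval is long against a 4-week course, and in a 60-patient trial a large part of the exposure can fall inside the first interval.

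The other safeguards work one event at a time. Skin irritation and severe muscle discomfort are named in advance as potential adverse events, so a series of them need not count as an unanticipated problem. For that kind of accumulation, the yearly review is the only planned look at the whole series. What is at stake is the timeliness of safety information. The primary analysis is not involved.

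**Working it through.** **Inputs from the protocol.** 60 recruited, 20% dropout, 48 completers, 24 per group (Sample Size Calculation); 4 weeks of treatment (Study Design); 5 sessions a week of 45 min (Interventions); review at least yearly (adverse event reporting section).

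**Assumptions.** 1:1 allocation, so about 30 NMES patients. Even accrual over A months. First review 12 months after the first patient enters. The protocol does not say when the year starts; counting from an earlier date, such as approval, would lower the shares below.

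**The plan's own figure.** 48 / (1 − 0.20) = 60, as stated.

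**Exposure per patient.** 5 × 4 = 20 sessions; 20 × 45 min = 15 h; 30 × 15 h = 450 h of planned NMES. Treatment lasts W = 28 / 30.44 = 0.92 months, about 8% of a 12-month interval.

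**Share of planned NMES exposure delivered by month 12.** A patient entering at month u has received min(W, max(0, 12 − u)) / W of the course. Averaged over even entry, this is 100% when A ≤ 12 − W = 11.1 months. For A of 12 months or more it is (12 − W/2) / A = 11.54 / A.

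**The same share at the first review under a trigger of 15 patients finished or discontinued.** Ignoring early discontinuations, the fifteenth patient enters at A/4 and finishes at A/4 + W. The share is then (A/4 + W/2) / A = 25% + 0.46 / A. This review precedes month 12 when A/4 + 0.92 ≤ 12, that is A ≤ 44.3 months.

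| Accrual A (months) | Share before month-12 review | First count-based review (month) | Share by then |
|---|---|---|---|
| 11 | 100% | 3.7 | 29% |
| 12 | 96% | 3.9 | 29% |
| 24 | 48% | 6.9 | 27% |
| 36 | 32% | 9.9 | 26% |
| 60 | 19% | 15.9 (annual minimum comes first) | 19% at month 12 |

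At least half of the exposure precedes month 12 when 11.54 / A ≥ 0.5, that is A ≤ 23.1 months, or at least 60 / 23.1 = 2.6 patients a month over both arms.

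**Dropout.** These are shares of planned exposure. The number who have finished the full NMES course by month 12 is 30 × 11.08 / A: 27.7, 13.9 and 9.2 for accrual over 12, 24 and 36 months. If the planned 20% dropout applies evenly, multiplying by 0.8 gives about 22, 11 and 7.

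**The case against.** The strongest defence is that little would in fact go unseen. Patients are contacted weekly. Severe discomfort or skin irritation leads to discontinuation of device use pending review. Events affecting safety are adjudicated for severity, expectedness and relatedness, and reporting runs on limits of 2 days to 1 week depending on the route. In a one-centre trial with about 30 NMES patients, the same few people see each event and may notice a run without a formal meeting. The yearly frequency is also a minimum, so earlier reviews are allowed. The institutional template in the protocol accepts a simple investigator-run plan for a minimal-risk study.

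Most of this stands, and it sets the limits of the point. A reader might infer that patients in this trial are unprotected, or that a run of non-serious events could never bring the review forward. The documents support neither. The early-review exception covers unanticipated problems as well as serious events, and an unexpected cluster might qualify; that depends on an institutional policy not reproduced in the protocol. A reader might also infer that treatment will be over before the first look. That depends on accrual, which is not stated, and at 36 to 60 months only 32% to 19% of exposure comes first.

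The defence does not supply a scheduled look across patients. Permission to review earlier is not a schedule, and handling events singly is a different task from judging their frequency. Low risk and small numbers may justify having no external board, but they do not explain a first scheduled look that could follow all treatment. The plan itself says NMES has hardly been studied soon after discharge and describes the training load as substantial.

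**Conclusion.** The point holds as a modest, inexpensive improvement. The only scheduled review across patients runs on a calendar that is unrelated to exposure. If accrual takes about two years or less, roughly half or more of the NMES exposure can precede a month-12 review, and all of it if accrual takes 11 months or less. With slow accrual the gap is small. The gap concerns only an accumulation of anticipated, non-serious events, because single events and serious or unanticipated ones have their own routes. The sizes rest on even accrual, 1:1 allocation and a first review 12 months after first entry. The plan contains no contradiction here.

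**What to change.** In the adverse event reporting section, schedule the pattern review after every 15 randomized patients have completed or discontinued the 4-week period, and at least annually, by the monitors already assigned. Discontinuations must count. With about 48 completers expected, a trigger on completers alone might never reach 60, and it would leave out patients who stop because of an event. Counted this way, reviews fall at 15, 30, 45 and 60 patients. The first three can inform later treatment and the fourth is a closing look. Each block of 15 holds about 7 or 8 NMES patients.

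The Randomization and blinding section blinds the PI and co-I, while PIs also have safety roles. The reviews should therefore use events pooled across arms where possible. Pooling cannot hide the arm for an event that only the device could cause.

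The exception for serious adverse events and unanticipated problems and the yearly progress reports stay as written. The cost is a few short extra reviews, with no new staff. If accrual takes longer than about 44 months, the annual minimum governs the first review and little changes.

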6 MW was developed to assess cardiopulmonary fitness in patients with lung and cardiac disease

(5), but has been used widely to assess disability in older adults (6) and is the most common metric used when seeking FDA approval for interventions to improve physical function. We have experience with this measure in heart failure patients (7).

Treatment phase

NMES will be carried out bilaterally on the quadriceps using a portable stimulator (EMPI Continuum). Two adhesive electrodes will be affixed to the anterior surface of each thigh: ~1 cm distal to the inguinal crease and ~5 cm proximal to the patella, just lateral to the midline of the thigh to assure that it does not interfere with incisions for vein harvest. Symmetrical, biphasic pulses (400 μ s duration at 25 Hz) will be used, with a duty cycle of 25% (10 s on, 30 s off). Patients will be trained to conduct NMES sessions and will select stimulation intensities sufficient to cause visible muscle contractions below their pain threshold. Training in the use of the NMES device will begin prior to day of discharge. . This training will consist of one session per day of ~15 min to familiarize the volunteer with the unit and the exercise/contraction stimulus. Upon discharge, NMES sessions will occur 5 d/wk once per day for 45 min per occasion (5 min low-intensity warm-up, 40 min higher-intensity stimulation) for 4 wks. This program is meant to mimic an aerobic-type exercise stimulus (8) and has been shown in heart failure patients to have functional benefits over a similar treatment period (9, 10). We acknowledge that the NMES training load is substantial, but have modeled this program on others that have shown morphological and functional effects in heart failure patients (11). At this exploratory stage, we feel that it is essential to use a stimulus that affects muscle size and function, with future studies modifying the NMES dose to establish a threshold that elicits a training effect with the highest subject compliance rate. Daily logs and weekly phone contacts will be used to track compliance, and compliance will be covertly monitored using the device software.

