Control patients will not receive an NMES device. We chose not to utilize a control NMES intervention (eg, stimulation below threshold to elicit contraction) to mitigate the possibility that patients may increase stimulation to produce muscle contractions if there is perceived benefit. Rigorous control over the NMES stimulus is preferable to controlling for any effects of sub-threshold, cutaneous electrical stimulation. Patients will be contacted weekly to assess their recovery and discuss issues related to general health to equate the degree of interaction with study personnel to that of the NMES intervention group.

Quality of Life measures: will be assessed with the following questionnaires which will be obtained at baseline (discharge) and 1 month following discharge

- a. Self-reported physical functioning assessment using the Medical Outcomes Study Short Form-36 (MOS SF-36) survey questionnaire (0-100 scale) with 100 representing excellent physical functioning
- b. Kansas City Cardiomyopathy questionnaire

Activities of Daily Living measures:

- a. Lawton Brody ADL questionnaire
- b. Katz Index of Independence in Activities of Daily Living

References cited above:

1. Ades, P. A., Savage, P. D., Cress, M. E., Brochu, M., Lee, N. M., and Poehlman, E. T. (2003) Resistance training on physical performance in disabled older female cardiac patients. *Med Sci Sports Exerc* **35**, 1265-1270
4. Rengo, J. L., Savage, P. D., and Ades, P. A. (in press) Directly measured physical function in cardiac rehabilitation. *J Cardiopulm Rehabil Prev*
5. Guyatt, G. H., Sullivan, M. J., Thompson, P. J., Fallen, E. L., Pugsley, S. O., Taylor, D. W., and Berman, L. B. (1985) The 6-minute walk: a new measure of exercise capacity in patients with chronic heart failure. *Can Med Assoc J* **132**, 919-923

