Volunteers will be withdrawn if the research team, clinician and/or safety officer feels that further participation in the study or performance of any procedure associated with this study would, in any way, put the volunteer at undue risk or not be in their best interest. Moreover, volunteers may be withdrawn if s/he fails to attend scheduled visits or do not comply with instructions from research staff.

Sources of Materials: Identify sources of research material obtained from individually identifiable human subjects in the form of specimens, records or data. Indicate whether the material or data will be obtained specifically for research purposes or whether use will be made of existing specimens, records or data.

An individual research record will be kept on each volunteer in compliance with HIPAA standards. This record will contain identifying data, demographic information and results from all clinical research measurements and evaluations. The results of all testing will be kept confidential. All materials gathered in conjunction with the proposed studies will be used for research purposes only and will be available only to research personnel working on these studies, who have obtained proper training in human subjects research and privacy protection.

DRUG AND DEVICE INFORMATION

Investigators are encouraged to consult the UVM Medical Center Investigational Pharmacy Drug Service ([name]) prior to finalizing study drug/substance procedures.

Drug (s)

Not applicable

Drug name – generic followed by brand name and common abbreviations. Availability – Source and pharmacology; vial or product sizes and supplier. If a placebo will be used, identify its contents and source. (attach investigational drug brochure)

Preparation: Reconstitution instructions; preparation of a sterile product, compounded dosage form; mixing guidelines, including fluid and volume required. Identify who will prepare.

Storage and stability – for both intact and mixed products.

Administration – Describe acceptable routes and methods of administration and any associated risks of administration.

Toxicity – Accurate but concise listings of major toxicities. Rare toxicities, which may be severe, should be included by indicated incidence. Also adverse interactions with other drugs used in the protocol regimen as well as specific foods should be noted. Address significant drug or drug/food interactions in the consent form as well. List all with above details.

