
Vulnerable Populations: *Explain the rationale for involvement of special classes of subjects, if any. Discuss what procedures or practices will be used in the protocol to minimize their susceptibility to undue influences and unnecessary risk (physical, psychological, etc.).*

Not applicable

Number of Subjects: *What is the anticipated number of subjects to be enrolled at UVM/UVM Medical Center and in the case of a multi-center study, with UVM/UVM Medical Center as the lead, the total number of subjects for the entire study.*

The proposed sample of 60 participants is based on having sufficient power to calculate differences in our primary outcome (6MW) between the control condition and the intervention and accommodating for potential drop outs (20%) from the study. We will need to recruit 60 patients with our target of 48 patients to complete the study

Inclusion/Exclusion Criteria: Eligibility and ineligibility criteria should be specific. Describe how eligibility will be determined and by whom. Changes to the eligibility criteria at a later phase of the research have the potential to invalidate the research.

Inclusion/Exclusion Criteria: Patients will be recruited if they: 1) have clinical diagnosis of heart failure being actively managed during hospitalization, 2) live within 30 miles of UVMMC and are between 50-90 years of age. Patients will be excluded if they have: 1) severe dementia/alzheimer's disease 2) an active malignancy, excluding non-melanoma skin cancer or low-grade prostate cancer under active surveillance; 3) exercise-limiting vascular or neuromuscular disease; 4) body mass index ≥ 40 kg/m² or 5*) an existing or history of deep vein thrombosis (DVT) or have an implantable cardioverter-defibrillator (ICD) or pacemaker (PPM).¹ *The last criteria is a contraindication for NMES and we will withdraw patients if they have an existing or history of deep vein thrombosis of the lower extremities or have an ICD or PPM

Literature cited:

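### Patients can be withdrawn from the study for non-compliance or an NMES-related problem, and the plan neither keeps their 4-week walk nor says that patients are analysed in their assigned arm

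*Combined protocol and SAP*

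**What the plan says.** All references are to the combined protocol and SAP.

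- **Withdrawal Procedures.** Withdrawal is required when staff judge that continuing would carry undue risk or not be in the patient's interest. In addition, "volunteers may be withdrawn if s/he fails to attend scheduled visits or do not comply with instructions from research staff". The template prompt asks what is required of a subject who withdraws; the answer gives nothing on this.
- **Data Safety and Monitoring.** After a problem related to NMES, an investigator will "decide whether continued participation in the study is in the best interest of the patient". The decision concerns the study, not only the device.
- **Adverse Event and Unanticipated Problem Reporting.** Severe discomfort or skin irritation leads to a pause in device use pending review. A separate judgement, after any adverse event, decides whether the participant continues in the study.
- **Procedures, Treatment phase.** NMES is 45 minutes a day, 5 days a week, for 4 weeks. The plan says: "We acknowledge that the NMES training load is substantial". It adds that "compliance will be covertly monitored using the device software". On the other side, "Control patients will not receive an NMES device".
- **Study Design.** "After completion of the 4 week intervention period, patients will undergo Post-Testing which will be identical to Baseline testing". This sets no adherence condition, and does not mention withdrawn patients.
- **Statistical Analysis.** ANCOVA, with the 4-week value as outcome and the discharge value as covariate. No analysis set, statement of analysis by assigned arm, or missing-data method is given.
- **Sample Size Calculation.** 60 recruited, 20% drop-out, 48 completers (24 per group).

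**The concern.** The Primary Aim asks whether NMES improves recovery compared with control. Randomisation protects that comparison only if patients are compared in the arms to which they were assigned and outcomes are sought from all of them.

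Here a patient's handling of the treatment after randomisation can end participation. The two routes at issue are not equally open to both arms. Only NMES patients can have an NMES-related problem, and most instructions that could be disobeyed, together with the device software that would reveal it, belong to the NMES regimen. No criterion limits when the non-compliance rule is used.

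If NMES patients who struggle with the device leave before the 4-week walk while comparable controls stay, the two analysed groups are no longer those that randomisation produced. The estimate is too high if the lost NMES patients would have walked worse than expected, and too low if they would have walked better.

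**Working it through.** **1. The plan's own figure.** Inputs from Sample Size Calculation: difference 50 m, SD 60 m, alpha 0.05 (two-sided reproduces the figure), power 80%. The two-sample t calculation gives 23.6, so 24 per arm, and 48 / (1 − 0.20) = 60. Power at 24 per arm is 0.807. The stated size reproduces, and it rests on patients who complete.

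**2. What happens to a withdrawn patient's walk.** The ANCOVA outcome is the 4-week value. A patient without one cannot enter the model, and no other method is named. No section asks withdrawn patients to return. The missed-visit clause adds little, because the contacts described between discharge and the final evaluation are weekly phone calls.

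**3. Illustration of size.** The loss pattern is assumed and has no source in the documents: 30 per arm, SD 60 m, baseline-to-4-week correlation r = 0.5, no true effect. Three NMES patients (10%) are non-compliers, being the lowest three on a latent score whose correlation with the baseline-adjusted walk is rho. Another 3 NMES and 6 control patients are lost at random, so 24 per arm remain.

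- Residual SD = 60 × √(1 − 0.5²) = 52 m.
- The lowest 3 of 30 standard normal values lie on average 1.86 SD below the other 27. Implied gap in walking distance = 1.86 × 52 × rho.
- Withdrawing the three raises the NMES mean by (3/30) × gap.

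| rho | Implied gap | Shift by formula | Simulated shift | Type I error |
|---|---|---|---|---|
| 0.3 | 29 m | 2.9 m | 3.0 m | 5.6% |
| 0.5 | 48 m | 4.8 m | 5.0 m | 6.1% |
| 0.7 | 68 m | 6.8 m | 6.7 m | 7.7% |

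The simulation used 8,000 runs (Monte Carlo error 0.17 m).

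- Walks of the same three patients kept: shift within 1 m of zero, type I error about 5%.
- Signs of rho reversed: −2.8, −5.1 and −6.6 m when withdrawn; within 1 m of zero when kept.
- Loss equal and equally informative in both arms: about 0 m.

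For scale, the standard error at 24 per arm is 52 × √(2/24) = 15 m, so a shift of 3 to 7 m is about 0.2 to 0.45 of a standard error. The plan cites 25 m as the minimal clinically significant difference.

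**4. What keeping these patients does to power.** If a share f of the NMES arm gains nothing, the effect of assignment is 50 × (1 − f). Two-sided t-test, SD 60 m:

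| Patients measured | Effect | Power, r = 0 | Power, r = 0.5 |
|---|---|---|---|
| 24 per arm (plan) | 50 m | 81% | 90% |
| 30 per arm, f = 10% | 45 m | 81% | 91% |
| 30 per arm, f = 20% | 40 m | 72% | 83% |
| 27 per arm, f = 10% | 45 m | 77% | 88% |
| 27 per arm, f = 20% | 40 m | 67% | 79% |

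The 27-per-arm rows assume that 10% of walks remain missing despite the effort.

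**The case against.** The non-compliance rule is discretionary and has no threshold. The plan treats compliance largely as something to measure: it is recorded by device software, feasibility is a stated purpose, and finding a dose with better compliance is left to future studies. That suggests non-compliers are meant to be observed, not routinely removed. Study Design promises post-testing with no adherence condition, and Statistical Analysis compares the study groups, which randomisation creates. No section defines a per-protocol or completer set or excludes a patient who has been tested. The section on adverse events does separate stopping the device from the decision on staying in the study. That decision, and withdrawal for undue risk or best interest, apply to both arms; in recently hospitalised heart failure patients they could matter as much as the device-related routes. Finally, the illustrated shift is small, and its upper end needs non-compliers to walk worse by more than the whole 50 m design effect.

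All of this stands, and it limits the point. A reader might infer that the plan prescribes a completer analysis, that the 12 planned drop-outs are non-compliers, or that the result will favour NMES. The documents support none of these: no completer set is named, nothing attributes the drop-outs to a cause, and nothing indicates how withdrawn patients would walk. What the objection does not supply is a sentence keeping a withdrawn patient's 4-week walk or placing patients in their assigned arm for analysis.

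**Conclusion.** The point holds in a limited form and should be fixed. This is more than missing detail: a stated rule can remove randomised patients for reasons tied to the assigned treatment, and nothing preserves their primary outcome. That the ANCOVA would then run on those still present is an inference from the model and from the silence on missing data.

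Size and direction of any bias are unknown. Under the assumptions shown, withdrawing three NMES non-compliers moves the estimate by about 3 to 7 m in either direction. In the favourable direction type I error is about 5% to 8%. That is modest beside a 15 m standard error, but keeping the walks avoids it.

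**What to change.** Leave the device-stopping and safety criteria as they are.

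1. Reword Withdrawal Procedures, and align Data Safety and Monitoring and the adverse-event section, so that non-compliance or stopping NMES does not by itself end follow-up. Every randomised patient in both arms is invited to the already planned 4-week assessment unless testing is unsafe or consent is withdrawn.
2. Add to Statistical Analysis that patients are analysed in their assigned arm whatever their adherence, and that losses are reported by arm and reason.
3. Add one simple sensitivity analysis for walks still missing that does not assume missing at random, for example a delta adjustment by arm.

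The cost is protocol wording, some effort to bring patients back for a visit already planned, and a little analysis. No new procedure is needed. The estimate is diluted when non-adherent patients stay in: at r = 0, power is about 81% to 72% with all 30 per arm measured and 10% to 20% of NMES patients gaining nothing, against the plan's 81%. It is lower if walks remain missing. Walks lost to death or refusal are not recovered by the rewording; only the sensitivity analysis addresses them.

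A separate item: the two Inclusion/Exclusion sections word withdrawal for clots and implanted devices differently. Under Methods and Procedures, "we will withdraw patients if they develop a blood clot or receive an ICD or PPM"; under Subject Characteristics, "we will withdraw patients if they have an existing or history of deep vein thrombosis of the lower extremities" or have such a device. The two must be reconciled.
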